### **3.2.4 Additional Inclusion and Exclusion Criteria for Selected Cohorts**

#### **3.2.4.1 Phase 1a**

Includes Phase 1a Dose Escalation, Phase 1a Exploration and Phase 1a 3-week Dosing Regimen cohorts

##### **3.2.4.1.1 Cabiralizumab Monotherapy Cohorts**

###### **Inclusion**

1. Histologically or cytologically confirmed solid tumor that is locally recurrent or metastatic and has progressed following standard treatment or is not appropriate for standard treatment
2. Patients with squamous NSCLC must have documented progression on nivolumab in order to enroll in the monotherapy cohorts of the study.

##### **3.2.4.1.2 Cabiralizumab + Nivolumab Combination Cohorts**

###### **Exclusion**

1. Prior exposure to any PD-1 pathway targeting drug
  - a. This will not apply to additional patients enrolled in Phase 1a after completion of the DLT period to fully characterize safety, PK, and PD.
2. Subjects with history of life-threatening toxicity related to prior immune therapy (e.g., anti-CTLA-4 or anti-PD-1/PD-L1 treatment or any other antibody or drug specifically targeting T-cell co-stimulation or immune checkpoint pathways) except those that are unlikely to re-occur with standard countermeasures (e.g., Hormone replacement after adrenal crisis)

### 3.2.4.2 Phase 1b

#### Exclusion

1. Subjects with a history of life-threatening toxicity related to prior immune therapy (e.g., anti-CTLA-4 or anti-PD-1/PD-L1 treatment or any other antibody or drug specifically targeting T-cell co-stimulation or immune checkpoint pathways) except those that are unlikely to recur with standard countermeasures (e.g., Hormone replacement after adrenal crisis)

#### 3.2.4.2.1 Cohort 1b1: Non-Small Cell Lung Cancer (PD-1 Naïve)

#### Inclusion

1. Patients with histologically or cytologically documented non-small cell lung cancer (NSCLC) who present with Stage IIIB locally advanced or Stage IV metastatic disease (according to version 7 of the International Association for the Study of Lung Cancer Staging Manual in Thoracic Oncology) or with recurrent or progressive disease following multi-modal therapy (radiation therapy, surgical resection, or definitive chemoradiation)
2. Objective evidence of disease progression during or after at least one ALK-targeting agent (if ALK mutation positive) or after at least one EGFR-targeting agent (if EGFR mutation positive) unless patient has refused these diagnostic tests or specific therapies.
3. Disease progression or recurrence during/after a platinum doublet-based chemotherapy regimen for advanced or metastatic disease
  - a. Maintenance therapy following platinum doublet-based chemotherapy is not considered a separate therapy regimen.
  - b. Patients who received platinum-containing adjuvant, neoadjuvant or definitive chemoradiation therapy given for locally advanced disease, and developed recurrent (local or metastatic) disease within 6 months of completing therapy are eligible.
  - c. Patients with recurrent disease > 6 months after platinum-containing adjuvant, neoadjuvant or definitive chemo-radiation therapy given for locally advanced disease, who also subsequently progressed during or after a platinum doublet-based regimen given to treat the recurrence, are eligible.

#### Exclusion

1. Has received prior therapy immune cell-modulating antibody regimens, such as, but not limited to anti-PD-1, anti-PD-L1, anti PD-L2, anti-CTLA-4, anti-CD137, anti-KIR, and/or anti-OX40 antibodies.

### 3.2.4.2.2 Cohort 1b2: Non-Small Cell Lung Cancer (De novo or Acquired Resistance to Anti-PD-1 Targeting Drugs)

#### Inclusion

1. Patients with histologically or cytologically documented NSCLC who present with Stage IIIB locally advanced or Stage IV metastatic disease.
2. Patient has radiological evidence of disease progression after receiving at least 2 doses of an anti-PD-1 targeting drug (e.g. nivolumab, pembrolizumab) in either of the following settings: progressive disease as the initial best objective response (de novo resistance), *or* progressive disease after an initial response of either CR, PR or SD (acquired resistance).
3. Objective evidence of disease progression during or after at least one ALK-targeting agent (if ALK mutation positive) or after at least one EGFR-targeting agent (if EGFR mutation positive) unless patient has refused these diagnostic tests or specific therapies.
4. Disease progression or recurrence during/after a platinum doublet-based chemotherapy regimen for advanced or metastatic disease.
  - a. Maintenance therapy following platinum doublet-based chemotherapy is not considered a separate therapy regimen.
  - b. Patients who received platinum-containing adjuvant, neoadjuvant or definitive chemoradiation therapy given for locally advanced disease, and developed recurrent (local or metastatic) disease within 6 months of completing therapy are eligible.
  - c. Patients with recurrent disease > 6 months after platinum-containing adjuvant, neoadjuvant or definitive chemo-radiation therapy given for locally advanced disease, who also subsequently progressed during or after a platinum doublet-based regimen given to treat the recurrence, are eligible.

#### Exclusion

1. Intolerance to any PD-1 targeting drug.

Intolerance is defined as any treatment-related Grade 4 AE, or any treatment-related Grade 2 or Grade 3 AE that is unacceptable to the patient and persists despite standard countermeasures.
2. Prior treatment with an mTOR inhibitor (including, but not limited to, everolimus, temsirolimus, sirolimus, and ridaforolimus).

### 3.2.4.2.3 Cohort 1b3: Squamous Cell Carcinoma of the Head and Neck

#### Inclusion

1. Patients with histologically or cytologically documented recurrent or metastatic squamous cell carcinoma of the head and neck (SCCHN) (oral cavity, pharynx, larynx), stage III or IV and not amenable to local therapy with curative intent (surgery or radiation therapy with or without chemotherapy).

2. Tumor progression or recurrence within 6 months of the last dose of platinum therapy in the adjuvant (i.e. with radiation after surgery), primary (i.e., with radiation), recurrent, or metastatic setting or patients that are intolerant to platinum chemotherapy.

### **Exclusion**

1. Histologically confirmed recurrent or metastatic carcinoma of the nasopharynx and any salivary gland or non-squamous histology.
2. Has received prior therapy immune cell-modulating antibody regimens, such as, but not limited to anti-PD-1, anti-PD-L1, anti PD-L2, anti-CTLA-4, anti-CD137, anti-KIR, and/or anti-OX40 antibodies.

#### **3.2.4.2.4 Cohort 1b4: Pancreatic Cancer**

### **Inclusion**

1. Histologically or cytologically documented unresectable localized, borderline resectable, locally advanced or metastatic adenocarcinoma of the pancreas, which has failed, or is not indicated for standard therapy, or for which the patient has refused standard therapy
2. Patients who may have received prior surgery, radiation therapy for the management of locally advanced or metastatic adenocarcinoma of the pancreas providing that disease progression has been documented. All toxicities should be resolved, and the last fraction of radiation treatment was completed at least 4 weeks prior to first study drug administration

### **Exclusion**

1. Patients with islet cell neoplasms, neuroendocrine or other primary tumors in the pancreas
2. Patients with active pancreatitis
3. Has received prior therapy immune cell-modulating antibody regimens, such as, but not limited to anti-PD-1, anti-PD-L1, anti PD-L2, anti-CTLA-4, anti-CD137, anti-KIR, and/or anti-OX40 antibodies
4. Ascites of Grade 2 or higher
5. Albumin <3.0 g/dL

#### **3.2.4.2.5 Cohort 1b5: Advanced Ovarian Cancer**

### **Inclusion**

1. Patients with histologically or cytologically confirmed epithelial ovarian cancer, fallopian tube, or primary peritoneal cancer.
2. Patients who have received at least three prior regimens of treatment.

**Exclusion**

1. Has received prior therapy immune cell-modulating antibody regimens, such as, but not limited to anti-PD-1, anti-PD-L1, anti PD-L2, anti-CTLA-4, anti-CD137, anti-KIR, and/or anti-OX40 antibodies.

**3.2.4.2.6 Cohort 1b6: Renal Cell Carcinoma****Inclusion**

1. Patients with histologically or cytologically confirmed advanced or metastatic renal cell carcinoma with a clear-cell component.
2. Must have received at least one prior anti-angiogenic therapy regimens (including, but not limited to, sunitinib, sorafenib, pazopanib, axitinib, tivozanib, and bevacizumab) in the advanced or metastatic setting. Prior cytokine therapy (eg, IL-2, IFN- $\alpha$ ), vaccine therapy, or treatment with cytotoxics is also allowed.

**Exclusion**

1. Has received prior therapy immune cell-modulating antibody regimens, such as, but not limited to anti-PD-1, anti-PD-L1, anti PD-L2, anti-CTLA-4, anti-CD137, anti-KIR, and/or anti-OX40 antibodies.

**3.2.4.2.7 Cohort 1b7: Malignant Glioma****Inclusion**

1. Histologically or cytologically documented advanced World Health Organization (WHO) Grade IV malignant glioma (glioblastoma or gliosarcoma).
2. Previous treatment with radiotherapy and temozolomide.
3. Documented first recurrence of GBM by diagnostic biopsy or contrast-enhanced MRI performed within 28 days of first study drug administration per Response Assessment in Neuro-oncology (RANO) criteria.
4. If on steroids, dose must be stable or decreased for a minimum of 5 days prior to baseline MRI.

**Exclusion**

1. Prior treatment with bevacizumab or another VEGF- or VEGFR-targeting agent.
2. Recent evidence of more than Grade 1 CNS hemorrhage on baseline MRI scan.
3. History or evidence upon physiological/neurological exam of CNS disease (e.g., seizures) unrelated to cancer unless adequately controlled by medication or potentially interfering with the study treatment.
4. Patients unable to have a head contrast-enhanced MRI due to a pre-existing medical condition including a pacemaker or implantable cardioverter defibrillator (ICD) device.

- 5. Has received prior therapy immune cell-modulating antibody regimens, such as, but not limited to anti-PD-1, anti-PD-L1, anti PD-L2, anti-CTLA-4, anti-CD137, anti-KIR, and/or anti-OX40 antibodies.

### 3.2.5 Women of Childbearing Potential

Women of childbearing potential (WOCBP) include any females who have experienced menarche and who have not undergone surgical sterilization (hysterectomy, bilateral tubal ligation, or bilateral oophorectomy), and who are not post-menopausal. Post-menopause is defined as:

- Amenorrhea  $\geq 12$  consecutive months without another cause, and a documented serum follicle stimulating hormone (FSH) level  $>35$  mIU/mL, *or*
- Women with irregular menstrual periods and a documented serum FSH level  $>35$  mIU/mL (*Note:* FSH level testing is not required for women  $\geq 62$  years old with amenorrhea of  $\geq 1$  year), *or*
- Women on hormone replacement therapy (HRT).

Women who are using oral or other hormonal contraceptives, such as vaginal products, skin patches, or implanted or injectable products, or mechanical products, such as an intrauterine device or barrier methods (diaphragm, condoms, spermicides) to prevent pregnancy or who are practicing abstinence or who have a sterile (e.g., vasectomy) partner should be considered to be of childbearing potential ([Gabbay 2008](#), [Kestelman 1991](#)).

[REDACTED]

[REDACTED]

[REDACTED]

[REDACTED]

[REDACTED]

[REDACTED]

[REDACTED]

[REDACTED]

[REDACTED]

[REDACTED]

[REDACTED]

- █ [REDACTED]
- █ [REDACTED]
- █ [REDACTED]

[REDACTED]

[REDACTED]

[REDACTED]

[REDACTED]

[REDACTED]

[REDACTED]

**3.4 Discontinuation of Patients following any Treatment with Study Drug**

Patients **must** discontinue study drugs for any of the following reasons:

- Withdrawal of informed consent (patient’s decision to withdraw for any reason)
- Any clinically significant AE, abnormal laboratory test results, or intercurrent illness which, in the opinion of the Investigator, indicates that continued participation in the study is not in the best interest of the patient
- Patients who are required to have prohibited concomitant medications

- Pregnancy
- Termination of the study by the Sponsor
- Loss of ability to freely provide consent through imprisonment or involuntary incarceration for treatment of a psychiatric or physical (e.g., infectious disease) illness
- Documented disease progression or clinical deterioration while receiving active study therapy
- Non-compliance by the patient

All patients who discontinue study treatment should comply with protocol specified follow-up procedures as outlined in Section 5.2.4. The only exception to this requirement is when a patient withdraws consent for all study procedures or loses the ability to consent freely (i.e., is imprisoned or involuntarily incarcerated for the treatment of a psychiatric or physical illness).

If a patient was discontinued, the reason for discontinuation must be entered on the appropriate CRF. The date and reason for cessation of cabiralizumab and/or nivolumab will be documented, and the Investigator must make every effort to perform the End-of-Treatment Visits. Adverse event reporting will continue until 100 ( $\pm 7$ ) days after the last dose of study drug or until initiation of subsequent anti-cancer therapy. Patients with ongoing SAEs will be followed until resolution or stabilization.

### **3.5 Long-Term Follow-up**

Patients who discontinue treatment while still receiving clinical benefit (i.e., CR, PR or SD) should get follow-up tumor scans every 12 ( $\pm 2$ ) weeks until disease progression or use of subsequent anti-cancer therapy to determine the duration of response, unless consent is withdrawn.

Long-Term Follow-up for survival may be conducted by telephone, rather than by an in-person visit, once tumor progression is determined or use of subsequent anti-cancer therapy has been initiated.

## 4. Study Drugs

In this study, both study drugs, cabiralizumab and nivolumab, are considered Investigational Medicinal Products (IMP).

### 4.1 Investigational Products

An investigational product, also known as investigational medicinal product in some regions, is defined as a pharmaceutical form of an active substance or placebo being tested or used as a reference in a clinical study, including products already having a marketing authorization but used or assembled (formulated or packaged) differently than the authorized form, or used for an unauthorized indication, or when used to gain further information about the authorized form. In this protocol, the investigational products are cabiralizumab and nivolumab.

### 4.2 Handling and Dispensing

The investigational product should be stored in a secure area according to local regulations. It is the responsibility of the Investigator to ensure that investigational product is only dispensed to Patients. The investigational product must be dispensed only from official study sites by authorized personnel according to local regulations.

The applicable site personnel should ensure that the study drugs are stored in accordance with the environmental conditions (temperature, light, and humidity) determined by the Sponsor. If concerns regarding the quality or appearance of the study drugs arise, do not dispense the study drugs and contact the Sponsor or designee immediately.

Study drug documentation including all processes required to ensure drug is accurately administered must be maintained. This includes documentation of drug storage and administration and, as applicable, storage temperatures, reconstitution, and use of required processes (e.g. required diluents, administration sets).

#### 4.2.1 Cabiralizumab

The investigational supply of cabiralizumab will be provided to the study centers by the Sponsor (or designee) and will be administered to patients in the clinical study by a trained healthcare professional.

Cabiralizumab drug product is supplied for IV administration as a sterile, aqueous, colorless to pale yellow liquid, clear to slightly opalescent pyrogen-free solution in 5 mL glass vials stoppered with coated stoppers, and equipped with aluminum seals. Light (few) particulates (consistent in appearance to proteinaceous particles) may be present. Each vial contains a minimum of 5 mL of a 20 mg/mL solution of cabiralizumab (approximately 100 mg per vial). Storage Conditions: 2–8°C (36–46°F). The vials will be provided in a carton. Both vials and cartons will be labeled per local regulations. Refer to the pharmacy manual for more specific information on the drug product.

## 4.2.2 Nivolumab

The investigational supply of nivolumab will be provided to the study centers by the Sponsor or designee. Refer to the Nivolumab Investigator's Brochure for preparation and storage conditions of nivolumab.

Care must be taken to assure sterility of the prepared solution as the product does not contain any antimicrobial preservatives or bacteriostatic agents. No incompatibilities between nivolumab and polyolefin bags have been observed.

## 4.3 Study Drug Dosing and Dose Modification

### 4.3.1 Dosing

For patients in the monotherapy cohorts, cabiralizumab infusion may be administered as a 30-minute IV infusion on Day 1 of each 14-day treatment cycle. For the combination therapy, nivolumab should always be administered first as a 30-minute IV infusion, with a 30- to 60-minute rest, followed by a 30-minute infusion of cabiralizumab (patients in 3-week dosing regimen cohort will receive study drugs on Day 1 of each 21-day treatment cycle). If any Grade 3 or higher infusion reaction is observed during the proposed infusion rate of nivolumab 3 mg/kg over 30 minutes, the infusion rate will be extended to 60 minutes for all current and subsequent patients for the duration of this study. Patients may be dosed no less than 12 days from the previous dose.

For Cohort 1aM2, 6 mg/kg cabiralizumab monotherapy, and dose escalation Cohorts 1aC2 and 1aC3, cabiralizumab and nivolumab combination therapy, the dose interval between the first and second patients in each cohort should be at least 24 hours for safety monitoring.

Dosing calculations should be based on the body weight assessed at Cycle 1 Day 1 prior to the first dose of study drug administration. It is not necessary to recalculate subsequent doses if the patient's weight is within 10% of the weight used to calculate the previous dose. All doses should be rounded to the nearest milligram.

Patients should be carefully monitored for infusion reactions during study drug administration. If an acute infusion reaction is noted, patients should be managed according to the guidelines in Section 4.3.10 [REDACTED]

Doses of study drugs may be interrupted, delayed, or discontinued depending on how the patient tolerates the treatment.

All vials are for single use only. Further instructions on study drug preparation and administration are provided in the Pharmacy Manual.

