## Study Design (cont.)

Phase 1a: 3-Week Dosing Regimen	An alternative dosing regimen cohort (1aD) with 10 patients has been added to characterize the PK and safety of cabiralizumab in combination with nivolumab when administered at a 3-week dosing schedule. In this cohort, 4 mg/kg cabiralizumab in combination with 3 mg/kg nivolumab will be administered intravenously every three weeks until disease progression, unacceptable toxicity, or other reason for treatment discontinuation. Patients who enter this cohort will follow eligibility criteria for Phase 1a. Patients will not be evaluated for DLT as the dose frequency is less than Cohort 1aC3 which has cleared the DLT window at the time of this amendment.
Phase 1a: Exploration Cohort	Based on emerging clinical and translational data, up to 40 patients will be included in Phase 1aE to further explore safety, PK, and PD at alternative dose levels or dosing schedules which have already successfully cleared their respective DLT periods. In each cohort, cabiralizumab either as monotherapy or in combination with nivolumab will be administered until disease progression, unacceptable toxicity, or other reason for treatment discontinuation. Patients who enter Phase 1aE will follow eligibility criteria for Phase 1a.
Phase 1b: Dose Expansion	Seven cohorts consisting of approximately 30 patients each in specific tumor types will characterize the safety and evaluate the efficacy at the RD of cabiralizumab in combination with nivolumab. In each cohort, 4 mg/kg cabiralizumab in combination with 3 mg/kg nivolumab will be administered intravenously every 2 weeks until disease progression, unacceptable toxicity, or other reason for treatment discontinuation.

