**Phase 1aC: Combination Dose Escalation Cohorts**

Cabiralizumab and nivolumab combination therapy in patients with advanced solid tumors

- Cohort 1aC1: cabiralizumab 1 mg/kg + nivolumab 3 mg/kg every 2 weeks
- Cohort 1aC2: cabiralizumab 2 mg/kg + nivolumab 3 mg/kg every 2 weeks
- Cohort 1aC3: cabiralizumab 4 mg/kg + nivolumab 3 mg/kg every 2 weeks
- Cohort 1aC4: cabiralizumab 6 mg/kg + nivolumab 3 mg/kg every 2 weeks

Alternative dose levels of cabiralizumab may be tested based on safety, PK and biomarker data. See Section 1.4 for cohort design and rationale.

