### 3.1.2 Treatment Period

#### 3.1.2.1 Phase 1a Monotherapy Cohorts and Combination Dose Escalation Cohorts

Phase 1a consists of three cabiralizumab monotherapy cohorts and four dose-escalation cohorts of cabiralizumab in combination with nivolumab with a minimum of 3 patients enrolled in each cohort. The planned dose levels and schedules for the Phase 1a cohorts are as follows:

- Cohort 1aM1: 2 mg/kg cabiralizumab, q2w
- Cohort 1aM2: 6 mg/kg cabiralizumab, q2w
- Cohort 1aM3: 4 mg/kg cabiralizumab, q2w
  - (Dose was de-escalated to 4 mg/kg after DLT observed in 1aM2 (See Section 1.9))
- Cohort 1aC1: 1 mg/kg cabiralizumab + 3 mg/kg nivolumab, q2w
- Cohort 1aC2: 2 mg/kg cabiralizumab + 3 mg/kg nivolumab, q2w
- Cohort 1aC3: 4 mg/kg cabiralizumab + 3 mg/kg nivolumab, q2w
- Cohort 1aC4: 6 mg/kg cabiralizumab + 3 mg/kg nivolumab, q2w

The 2 mg/kg cabiralizumab monotherapy cohort (1aM1) was enrolled first, followed by enrollment in the 1 mg/kg cabiralizumab and nivolumab combination cohort (1aC1). Both cohorts cleared without any DLTs. The 2 mg/kg cabiralizumab and nivolumab combination cohort (1aC2) started after the DLT period cleared in the 1 mg/kg cabiralizumab and nivolumab combination cohort and 2 mg/kg cabiralizumab monotherapy cohort.

The 6 mg/kg cabiralizumab monotherapy cohort (1aM2) opened after the DLT period cleared in the 2 mg/kg cabiralizumab monotherapy cohort (1aM1). There were two DLTs in patients treated in the 1aM2 cohort, both due to laboratory abnormalities. Subsequently, the dose was de-escalated and Cohort 1aM3 (4 mg/kg cabiralizumab monotherapy) was opened. There were two DLTs in the 1aM3 monotherapy cohort and the protocol was subsequently amended to allow higher cutoffs for these laboratory values (see Section 1.8.1). Additional patients were added to the 1aM3 cohort to evaluate the DLT period under the new criteria.

The 4 mg/kg cabiralizumab and nivolumab combination cohort (1aC3) was opened after the DLT period cleared in the 1 mg/kg and 2 mg/kg cabiralizumab and nivolumab combination cohorts and in the respective cabiralizumab monotherapy cohorts.

The 1aM2 cohort was also re-opened with the new DLT criteria. Upon successful completion of the DLT period the 6 mg/kg cabiralizumab and nivolumab combination cohort (1aC4) may be opened.

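### The 24-hour gap between first and second patients in Section 4.3.1 is not required for 1aC4, the highest planned combination dose

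*Protocol*

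**What the plan says.** Protocol Section 4.3.1 sets the rule by naming cohorts: "For Cohort 1aM2, 6 mg/kg cabiralizumab monotherapy, and dose escalation Cohorts 1aC2 and 1aC3, cabiralizumab and nivolumab combination therapy, the dose interval". The requirement itself is that "the dose interval between the first and second patients in each cohort should be at least 24 hours for safety monitoring". The only cohorts it reaches are 1aM2, 1aC2 and 1aC3.

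The synopsis list of combination escalation cohorts ends with "Cohort 1aC4: cabiralizumab 6 mg/kg + nivolumab 3 mg/kg every 2 weeks". Sections 3.1 and 3.1.2.1 list the same cohort, and SAP Section 7.1 gives it its own efficacy reporting group. Just below its list, the synopsis adds "See Section 1.4 for cohort design and rationale"; Section 1 is not visible in the public text.

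On timing, the synopsis paragraph on the 3-week regimen refers to "Cohort 1aC3 which has cleared the DLT window at the time of this amendment". Section 3.1.2.1 says of the 6 mg/kg monotherapy cohort: "The 1aM2 cohort was also re-opened with the new DLT criteria". It then says: "Upon successful completion of the DLT period the 6 mg/kg cabiralizumab and nivolumab combination cohort (1aC4) may be opened".

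**The concern.** The sentence in 4.3.1 names cohorts that had already started by this protocol version and leaves out the one planned escalation cohort still to open. The result is hard to reconcile: the interval applies when 6 mg/kg cabiralizumab is given alone, but not when nivolumab is added to that dose.

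What is at stake is a participant-safety precaution, not an analysis. Section 4.3.10 recognises that either drug may cause infusion or hypersensitivity reactions, and Section 4.3.1.1 recommends no nivolumab premedication in the first cycle. The study plans about 50 centres, and nothing visible stops the first two 1aC4 patients from being dosed on the same day. Section 4.3.10 asks for Grade 3 or 4 infusion reactions to reach the Medical Monitor within 24 hours. A second patient dosed at another centre inside that time could therefore be treated before the first patient's reaction was known.

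**Working it through.** The plan gives no figure to reproduce. The check classifies the seven escalation cohorts (synopsis; Sections 3.1 and 3.1.2.1) and compares them with the list in 4.3.1.

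| Cohort | Cabiralizumab dose | Role | Fold step | Named in 4.3.1 |
|---|---|---|---|---|
| 1aM1 | 2 mg/kg alone | monotherapy start | – | no |
| 1aM2 | 6 mg/kg alone | up from 2 | 6/2 = 3 | yes |
| 1aM3 | 4 mg/kg alone | de-escalation from 6 | – | no |
| 1aC1 | 1 mg/kg + nivolumab | combination start | – | no |
| 1aC2 | 2 mg/kg + nivolumab | up from 1 | 2/1 = 2 | yes |
| 1aC3 | 4 mg/kg + nivolumab | up from 2 | 4/2 = 2 | yes |
| 1aC4 | 6 mg/kg + nivolumab | up from 4 | 6/4 = 1.5 | **no** |

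Four cohorts are upward steps and three of them carry the interval; 1aC4 is the exception. Of the other unnamed cohorts, two are starting doses and one is a de-escalation. Section 4.4 can be read as treating 1aM3 as an escalation, but the study history in the synopsis and Section 3.1.2.1 both say it was opened after DLTs at 6 mg/kg.

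**Do the gates before 1aC4 explain the difference?**

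- 1aC2 opened after 1 mg/kg with nivolumab and 2 mg/kg alone (its own dose) had cleared. The interval was required.
- 1aC3 opened after the two lower combinations and the respective monotherapy cohorts had cleared. The interval was required.
- 1aC4 may open after re-opened 1aM2 (its own dose alone) completes its DLT period, with 1aC3 already cleared. The interval is not required.

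The safety teleconference (3.1.2.1) and the Cohort Review Committee (Section 8) apply to all three. The gating is alike and only the interval differs.

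**What could 24 hours reveal?** For combination patients, the Day 2 visit (5.2.2.3) has a PK sample, AE reporting and concomitant-medication review. Safety laboratory tests after Cycle 1 Day 1 are next scheduled on Day 8 (5.2.2.5). The interval can therefore bring out acute clinical events, but not routinely laboratory changes. The Day 2 window is 24 ± 6 hours, so the review may fall at 18 to 30 hours. A bare 24-hour gap does not guarantee that the review has taken place.

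**Cost.** The added wait is at most 1 day: 1/28 = 3.6% of the DLT window, or 1/42 = 2.4% if the window is extended to 42 days.

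**The case against.** **The list may be deliberate.** It names three of seven escalation cohorts, omits the first combination cohort, and nowhere says that every upward step is covered. This stands in part. The pattern is inferred, and the statement that 1aC4 is the only uncovered upward step holds only among cohorts with defined doses. Section 3.1.2.1 allows alternative dose cohorts, and Appendix E lists a 1aM4 with no dose.

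**1aC4 is the best-supported step.** Both adjacent regimens must have cleared, and the 1.5-fold step is the smallest. Phase 1b uses 4 mg/kg with nivolumab and may run alongside continued Phase 1a exploration (3.1.2.5), so experience just below 1aC4 could be larger than it was for earlier steps. This lowers the residual risk. It does not account for the omission, because 1aC2 and 1aC3 passed the same kind of gates and still had the interval.

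**Acute reactions are already watched for.** Section 5.2.2.2 schedules vital signs after nivolumab and at 10, 30 and 60 minutes after cabiralizumab, plus a 4-hour blood draw. Section 4.3.10 gives management rules, and the teleconference or committee could set an interval case by case. All this is true and narrows what the missing words would add. None of it separates the first two patients.

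**Unseen text.** Section 1 and the dose table are not visible, and a reason or further wording for 1aC4 could be there. This limit stands, although the sentence in 4.3.1 is intact.

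**Stronger readings that the documents do not support:**

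- A reader might infer that the interval would guard against the toxicity already seen at 6 mg/kg. Section 3.1.2.1 says: "There were two DLTs in patients treated in the 1aM2 cohort, both due to laboratory abnormalities". A 24-hour gap would not be expected to catch such events, given the Day 8 laboratory schedule.
- A reader might put a number on the patients protected. The visible documents give no acute-reaction rate at this dose and do not say how often the second patient would be dosed within 24 hours. Any assumed event rate is only an upper bound on the benefit.
- A reader might infer a proven drafting oversight. The visible text does not show whether the omission was intended.

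**Conclusion.** The point holds as a modest gap in a safety precaution. As 4.3.1 is written, the interval is not required at the highest planned combination dose. It is required at the same cabiralizumab dose alone and was required at both lower combination steps. Among cohorts with defined doses, 3 of 4 upward steps are covered and 1aC4 is not.

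The benefit of covering it is limited to acute infusion or hypersensitivity events where the second patient would otherwise be dosed within 24 hours. How often both conditions would be met cannot be estimated from the documents. No endpoint, sample size or analysis changes. The conclusion assumes that the unseen Section 1 and dose table do not extend the interval to 1aC4 or give a reason for exempting it. This is a cheap improvement, not a flaw that undermines the dose escalation.

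**What to change.** In Section 4.3.1, add 1aC4 to the cohorts in the 24-hour sentence, together with any later dose level above those already cleared. The second part covers the alternative doses that 3.1.2.1 permits, so the list need not be revised each time a cohort is added. If the sponsor has a reason to exempt 1aC4, state it in the same place.

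The cost is one sentence of protocol text and at most a 24-hour wait for one patient per cohort. The SAP needs no change.
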